## List of abbreviations

AE	Adverse Event
ALPS	Antenatal Betamethasone for Women at Risk for Late Preterm Delivery
BGC	Blood Glucose Concentration
CRF	Case Report Form
CS	Caesarean Section
DMC	Data Monitoring Committee
GA	Gestational Age
IQ	Intelligence Quotient
HRC	Health Research Council
MFM	Maternal Fetal Medicine
NICU	Neonatal Intensive Care Unit
NNU	Neonatal Unit
RCT	Randomised Controlled Trial
RDS	Respiratory Distress Syndrome
RR	Relative risk
SAE	Serious Adverse Event
SAR	Serious Adverse Reaction
SUSAR	Suspected Unexpected Serious Adverse Reaction
TSC	Trial Steering Committee
TTN	Transient tachypnoea of the newborn

## **1. LAY SUMMARY**

In New Zealand and Australia, over 50 000 babies are born by planned caesarean section (CS) each year and rates continue to rise. Planned CS poses some risk to babies, in particular, the need for admission to the neonatal unit (NNU) for breathing support which means mothers are separated from their baby.

When given to mothers expecting a preterm birth, corticosteroid injections save babies' lives and improve neonatal and childhood health. This knowledge has led clinicians to prescribe corticosteroids before a planned CS at or near term. Limited research in this area has shown that as well as benefits on neonatal breathing corticosteroids may lower baby's blood sugar levels and so possibly cause harm.

[figure not shown]
The C\*STEROID Trial is a multi-centre, placebo-controlled, randomised trial across New Zealand and Australia able to assess the effects of corticosteroids on newborn and childhood health when given to mothers prior to a planned CS at or near term. It will provide the first high-quality evidence on the balance between benefit and harm of corticosteroids in this setting. It will reliably inform clinical practice for more than one in ten of all future births in New Zealand and Australia.

## 2. BACKGROUND

### 2.1 Rationale

The rate of birth by planned, also referred to as elective and pre-labour, CS continues to rise each year and now accounts for more than one in ten births and over 50 000 babies born in New Zealand and Australia each year (Figure 1). Compared to vaginal birth, CS poses additional risks to baby. Most specifically respiratory morbidity, often referred to as respiratory distress syndrome (RDS) and transient tachypnoea of the newborn (TTN). Term and late preterm babies rarely die from these conditions which are typically self-limiting, but often require neonatal unit (NNU) admission for monitoring and/or respiratory support. This separates mother and baby interfering with breastfeeding and bonding.

**Figure 1.** Rates of CS in New Zealand 2008-2017.

Neonatal respiratory morbidity after birth by pre-labour planned CS is increased 7-fold compared with infants born vaginally and 3-fold compared with infants born by CS once labour has established. Gestational age at birth also contributes to this increased risk (Figure 2); hence, national practice guidelines recommend planned CS should occur  $\geq 39^{+0}$  weeks. However, planned CS at late preterm or early term gestation may still be necessary on maternal and/or fetal grounds, and planned CS at  $39^{+0}$  to  $39^{+6}$  weeks still imposes a 2-fold increase in neonatal respiratory morbidity.

[figure not shown]
**Figure 2.** Neonatal respiratory morbidity after elective CS compared to intended vaginal birth (reference) by gestational age.

Gestational Age	Adjusted Odds Ratio	95% CI
37 weeks	3.7	2.2-6.1
38 weeks	3.0	2.1-4.4
39 weeks	1.9	1.2-3.0
40 weeks	0.9	0.2-3.7

Corticosteroids accelerate fetal lung maturation by enhancing alveolar type II pneumocyte cell maturation and surfactant production; improve anti-oxidant activity and reduce pro-inflammatory cytokine production, thereby reducing short-term neonatal respiratory morbidity. A large body of evidence from over 30 randomised trials supports the administration of corticosteroids prior to preterm birth at <35+0 weeks gestation, regardless of mode of birth, to reduce perinatal death, RDS and other measures of neonatal adverse outcome with no evidence of later harm. What is less clear is if their use at gestational ages ≥35 weeks, and specifically prior to planned CS, provides benefit without harm.

A 2016 systematic review has identified six randomised trials for all modes of birth, planned or expected, ≥35 weeks gestation of antenatal corticosteroids compared to placebo (n=3 trials) or no treatment (n=3 trials). Three trials were specific to planned CS at term, ≥37+0 weeks, and three included women at risk of late preterm birth for all modes of birth at 34+0 to 36+6 weeks. Meta-analysis of all trials demonstrates that corticosteroid use reduces the incidence of RDS (5.5% vs 7.2%, RR 0.74 95%CI 0.61-0.91) and TTN (5.9% vs 9.1%, RR 0.56 95%CI 0.37-0.86) (Figure 3). A 2018 Cochrane Review of four randomised trials of corticosteroid use prior to planned CS at ≥37+0 weeks (three trials were also included in the 2016 review) found lower overall rates of respiratory morbidity, consistent with later gestation, but greater benefit than for late preterm births appearing to halve the risk of respiratory morbidity (RDS 0.8% vs 1.7%, RR 0.48 95%CI 0.27-0.87 and TTN 2.3% vs 5.3%, RR 0.43 95% CI 0.29-0.65). Consequently leading to fewer admissions to neonatal special care overall (3.0% vs 5.3% RR 0.62; 95% CI 0.43- 0.89) and for respiratory complications (2.4% vs 5.0%, RR 0.45 95% CI 0.22-0.90).

**Figure 3.** Effect of maternal corticosteroid use after 34+0 weeks gestation on RDS (all trials).

These systematic reviews suggest benefit, at least in the short term. However, for all trials specific to planned CS, the risk of bias was moderate and the GRADE quality of evidence was low indicating that the true effect of corticosteroids may be substantially different than the estimate of effect given. Furthermore, recent commentaries and reviews highlight the potential for harm, supported by an unanticipated finding of the Antenatal Betamethasone for Women at Risk for Late Preterm Delivery (ALPS) trial. This is the largest trial to date, including 2827 women at high risk of imminent birth at 34+0-36+6 weeks, and although respiratory morbidity was significantly reduced, the rates of neonatal hypoglycaemia were significantly higher in babies exposed to corticosteroids (22.8% vs 14.2%, RR 1.6 95% CI 1.4-1.9). Blood glucose was not

systematically measured in all babies in the ALPS trial and only recorded as an outcome in babies requiring NNU admission; thus, it is possible that this outcome is confounded. Nevertheless, it is physiologically plausible that maternal corticosteroid use may cause neonatal hypoglycaemia.

Neonatal hypoglycaemia has been associated with a variety of brain abnormalities seen on ultrasound and MRI, and recent but accumulating evidence suggests that even transient and treated neonatal hypoglycaemia is associated with adverse childhood outcomes. A 2019 systematic review has identified nine cohort studies exploring the later effects of hypoglycaemia in children who were born 'at-risk'. Although the quality of these studies was deemed low, significant effects on early childhood visual-motor and executive function and mid-childhood neurodevelopment, literacy and numeracy are evident, making the finding in the ALPS trial a major concern which requires further consideration and evaluation.

The risk of neonatal hypoglycaemia after corticosteroids prior to planned CS birth  $\geq 37^{+0}$  weeks is unknown as none of the randomised trials to date have reported rates of hypoglycaemia. There are no high quality data on later benefit or harm associated with term and late preterm use of corticosteroids. Only one trial with limited follow-up (37%) has reported childhood outcomes after corticosteroids prior to planned CS  $\geq 37^{+0}$  weeks, with a suggestion of poorer academic performance at 8-15 years of age after maternal corticosteroid use.

Advice from national and international guidelines in this area is limited and conflicting. Until recently the UK RCOG guideline recommended their use for planned CS  $\leq 38^{+6}$  weeks. This guideline now has been archived and its replacements give no guidance on this common clinical dilemma. The ACOG recommends use for all births at  $34^{+0}$  to  $36^{+6}$  weeks but again no advice is given for planned CS  $> 36^{+6}$  weeks. Data from our own work show significant variation in practice across New Zealand with some units routinely offering corticosteroids prior to all planned CS birth  $\leq 38^{+6}$  weeks, despite the 2015 guidelines from Australia and New Zealand concluding there is insufficient evidence to make a recommendation for planned CS  $> 34^{+6}$  weeks. However, these guidelines do include a research recommendation calling for randomised trials to investigate the neonatal effects and childhood disability rates when corticosteroids are administered to women prior to planned CS at term.

**There is insufficient evidence to guide practice on corticosteroid use prior to planned CS at late preterm and term gestational ages. There is low quality evidence on neonatal respiratory morbidity, minimal evidence on long-term effects and no evidence on neonatal hypoglycaemia.**

**The C\*STEROID Trial is a large multicentre randomised placebo controlled trial with sufficient power to assess both potential beneficial (respiratory) and harmful (hypoglycaemia) effects of corticosteroids prior to planned CS at  $35^{+0}$  to  $39^{+6}$  weeks and from this, to establish a randomised cohort able to assess the childhood benefits and/or harm of this intervention.**

## **2.2 Feasibility to undertake the C\*STEROID Trial**

The C\*STEROID Trial concept was developed by a multi-disciplinary group facilitated by experts in the field, clinicians, biostatisticians, consumers and a Māori research advisor at the annual ON TRACK Network Concept Development Workshop in 2017.

Through ON TRACK Network, we have engaged with district health boards (DHBs) around New Zealand, undertaking a survey 'Opinions & Current Practice in Antenatal Corticosteroid Administration Prior to Planned Caesarean Section Delivery from 35+0 Weeks Gestation'. We received responses from 15/18 DHBs which have 40 000 births annually with planned CS rates varying from 7.9% to 18.0% (over 4500 births each year). Thirteen units reported experience of participation in multi-centre trials and seven units currently employ research staff. Betamethasone is the corticosteroid of choice in all units. Thirteen units have a guideline for newborn blood glucose monitoring and all 15 units have a guideline for the management of hypoglycaemia. At that time 11 units expressed willingness to participate in the C\*STEROID Trial and a further five units expressed interest in participation; no units were unwilling to consider participation. Subsequently 14 New Zealand maternity units have provided letters of intent to participate to support Health Research Council funding applications.

We have also completed a local consumer feasibility survey of women booked for a planned CS at 35+0 to 39+6 weeks at Auckland District Health Board (ADHB) to explore attitudes to corticosteroid use prior to planned CS and to assess engagement in our research. ADHB guidelines follow bi-national guidelines that do not support the use of corticosteroids prior to planned CS  $\geq 35$  weeks. Women were provided with written information about corticosteroids and planned CS and an anonymous questionnaire. Of 63 responses, 48 (76%) had planned CS  $\geq 39^{+0}$  weeks. The majority of women (53/63, 84%) reported that the risks of CS had been explained to them by their maternity care provider but the use of corticosteroids had only been discussed with five women and offered to two. After provision of information regarding corticosteroids and planned CS, 11 (17%) women identified that, if offered, they would definitely or probably accept corticosteroids in their current pregnancy, 28 (44%) were unsure and 23 (37%) identified maybe or not at all as their response. In keeping with our previous work exploring consumer attitudes to corticosteroids at preterm gestations, women identified lack of information about risks and benefits as an important factor determining their decision. Of all respondents, 51% of women undergoing planned CS  $\geq 35^{+0}$  weeks would consider participating in a trial. Of these, the vast majority would be willing for their baby to undergo blood sugar testing in the first few days after birth (26/30, 87%).

From July 2019 to March 2020 we have completed a nine-month randomised C\*STEROID Feasibility Study. This was originally planned as a 12-month study but recruitment closed at the start of New Zealand's Level 4 COVID-19 lockdown with all objectives achieved. The study was funded by Cure Kids, Lottery Health Research New Zealand, the Hugo Charitable Trust and the University of Auckland Faculty Research Development Fund. Recruitment occurred at three sites (Auckland City, Tauranga and Waikato hospitals). With the same eligibility criteria as for the C\*STEROID Trial, the primary outcome was recruitment rate. Women were invited to participate and/or complete a questionnaire exploring the reasons women chose to, or not to, participate in the trial. Focus groups for clinicians and site researchers explored barriers and enablers to trial participation and completion allowing trial systems to be as efficient and effective as possible for a wider roll-out. The randomisation service, drug allocation and data collection system, trial drug production and packaging, standard operating procedures, and clinician and participant engagement resources were funded and successfully established for C\*STEROID Trial during the Feasibility Study. As planned *a priori*, we have remained blinded to outcome data by treatment

group for the C\*STEROID Feasibility Study allowing data to contribute to the main C\*STEROID Trial (n = 88 mothers and 92 babies).

A further practitioner survey including all Fellows of the Royal Australian and New Zealand College of Obstetricians and Gynaecologists has been undertaken in 2020. This provides up-to-date information on practitioner's views of corticosteroid use prior to planned CS at late preterm and term gestations, as well as attitudes towards the C\*STEROID Trial and expressions of interest to participate from Australian sites. There were 253 responses from Australian obstetricians including those working in all states; metropolitan, regional and rural areas; and across both public and private practice. A total of 107 Australian respondents expressed interest in participation in the C\*STEROID Trial and this is expected to cover at least 30 different maternity units.

### **3. TRIAL HYPOTHESIS & AIMS**

#### **3.1 Hypothesis**

The maternal administration of betamethasone compared to placebo prior to planned CS at 35+0 to 39+6 weeks gestation will reduce the risk of neonatal respiratory distress without increasing the risk of neonatal hypoglycaemia.

#### **3.2 Aims**

**Primary Aim:** To measure the effect of maternal betamethasone compared to placebo on the incidence of neonatal respiratory distress and on neonatal hypoglycaemia.

**Secondary Aims:** To measure the effect of maternal betamethasone compared to placebo therapy on:

- (i) the neonate: NNU admission, NNU duration of stay and breastfeeding at six weeks of age;
- (ii) the mother: postnatal infection and maternal wellbeing; and
- (iii) to establish a cohort of sufficient size to assess benefit and/or harm at 6-7 years of age in a later childhood outcome study exploring executive function, body size, and respiratory, cardiovascular and metabolic wellbeing.

### **4. TRIAL & DRUG SAFETY**

#### **4.1 Potential Risks to the Baby**

Antenatal corticosteroids including betamethasone are used as standard practice for mothers at high risk of preterm birth at <35+0 weeks gestation to provide protection against RDS, perinatal death and other measures of neonatal adverse outcome with little or no evidence of later harm. Previous research suggests that it may provide protection against respiratory conditions at later gestational ages and specifically when given before planned CS. This trial will assess other risks to the baby, in particular, neonatal hypoglycaemia. To date, no trials of corticosteroids prior

to planned CS at term or near term gestational ages have included data on rates of neonatal hypoglycaemia or included its measurement as a standard of the protocol.

#### **4.2 Potential Risks to the Mother**

The use of maternal corticosteroids may impose risk relating to infection morbidity. This has not been seen in previous trials. However, to date no trials of corticosteroids prior to planned CS only at term or near term gestational ages have included data on maternal outcomes including any infection. This trial will assess and quantify maternal infection risk.

### **5. STUDY DESIGN**

The C\*STEROID Trial is a multi-centre, triple-blind, placebo controlled, parallel, phase III trial with randomisation at participant level (1:1 allocation ratio).

#### **5.1 Trial Setting**

This trial will be conducted at maternity units across New Zealand and Australia. 14 of 20 district health boards in New Zealand have expressed interest in participation and provided support for the Health Research Council funding application. A request for expressions of interest for Australian sites has been made via a survey distributed to all fellows of the Royal Australian and New Zealand College of Obstetricians and Gynaecologists and obstetricians from at least 30 maternity units have expressed willingness to participate.

#### **5.2 Trial Co-ordination**

The trial will be coordinated by staff at The University of Auckland including the C\*STEROID Trial Principal Investigator and Lead Investigators, Clinical Research Coordinator(s), research midwives, PhD student(s) and any other staff required to support clinical trial activities or analysis.

### **6. STUDY POPULATION – Inclusion & Exclusion Criteria**

Women for whom CS is planned pre-labour at 35+0 to 39+6 weeks gestation will be identified from antenatal clinics and booked CS operating lists at each recruiting site.

#### **6.1 Inclusion Criteria:**

- Planned pre-labour CS  $\geq 35^{+0}$  - 39+6 weeks gestation
- $\geq 24$  hours\* and  $< 7$  days until planned birth
- Singleton or twin pregnancy with a live fetus

\*At the point of randomisation it must be  $\geq 24$  hours until the planned CS date and time for the participant to be eligible. This is to allow two doses of study drug to be administered, at 24 hours

(+/- 4 hours) apart, prior to the planned CS date and time (refer to section [10.3 Drug Administration](#)).

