## **9. RANDOMISATION**

Eligible women who have provided written, informed consent to participate will be enrolled by clinicians and research staff using a web-based randomisation service operating at the Clinical Data Research Hub Research Hub (CDRH) hosted by the Liggins Institute, The University of Auckland.

Randomisation will be stratified for;

1. Gestational age at planned caesarean section 35+0-36+6, 37+0-38+6, 39+0-39+9 weeks
2. Recruiting site
3. Singleton or twin pregnancy

Women will be randomised in a 1:1 ratio to betamethasone:placebo.

The randomisation process will assign each participant with a unique study ID number. This study ID number will be required when allocating study drug treatment pack and for recording data on the CRF. The randomisation service provides 24 hour access, 7 days per week. If a woman is found not to be eligible for the trial when her details are entered into the randomisation program the program will return a screen failure notification.

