### **10.3 Drug Administration and Assessment of Compliance**

The study drug will be administered by intramuscular injection, to the thigh, arm or buttock, by appropriately qualified clinical or research staff at the study site within seven days prior to planned CS. Two doses of study drug should be administered 24 hours apart +/- 4 hours (i.e. 20-28 hours). If the date/time of the participant's CS is brought forward and/or labour commences spontaneously before the second dose has been administered it should still be given as long as it is ≥20 hours following the first dose. If birth is planned (CS) or inevitable (spontaneous labour) and it is <20 hours since the first dose the second dose should not be given. There is no minimum timeframe between the second dose and the planned CS (or expected birth). The timing of each dose and compliance will be recorded on the CRF.

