## **11. TREATMENT DURATION/INDICATIONS TO STOP TREATMENT**

### **11.1 Treatment Duration**

Randomised participants will be given the first dose of study drug within seven days of their planned CS and a second dose 24 hours (+/- 4 hours) later. The first dose of study drug should be scheduled to allow for the administration of two doses 24 hours (+/- 4 hours) apart prior to the participants planned CS. No further doses of study drug or antenatal corticosteroids will be given, even in the event of a delayed planned CS date.

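### Women can be given blinded drug from just after 34+0 weeks, and if birth then becomes expected before 35+0 the protocol's bar on further antenatal corticosteroid conflicts with its own standard-practice statement

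*Protocol*

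**What the plan says.** Section 6.1 states the gestational criterion as "Planned pre-labour CS" between 35+0 and 39+6 weeks. It adds a timing criterion of at least 24 hours and fewer than 7 "days until planned birth". The footnote fixes when the 24 hours are counted: "At the point of randomisation it must be" at least that long until the planned date and time. Section 9 stratifies on "Gestational age at planned caesarean section". Section 6.2 excludes nobody on gestation, but does exclude women who have already had intramuscular corticosteroid for fetal lung maturity in this pregnancy. Sections 10.1, 10.3, 11.1 and 12.1.4 time the doses only against the planned caesarean.

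On the value of treatment, section 4.1 says that antenatal corticosteroids "are used as standard practice for mothers at high risk of preterm birth at" less than 35+0 weeks. Section 2.1 says that a large body of trials supports them before birth at that gestation, "regardless of mode of birth, to reduce perinatal death, RDS and other measures of neonatal adverse outcome".

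Section 10.3 covers the case where the caesarean "is brought forward and/or labour commences spontaneously before the second dose has been administered", but only to say whether the second study dose is given. Section 11.1 then says: "No further doses of study drug or antenatal corticosteroids will be given, even in the event of a delayed planned CS date".

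**The concern.** The protocol uses 35+0 in two ways. As an eligibility limit it refers to the planned birth. As the boundary of established treatment it refers to the birth that is actually expected. The two agree as long as the plan holds. They separate when a woman randomised before 35+0 goes into labour, or has her caesarean moved, so that birth is expected before 35+0.

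Such a woman may have received placebo only and, because of the exclusion in section 6.2, no earlier corticosteroid for lung maturity. Her blinded clinician would find one section calling corticosteroids standard practice for this birth, another barring them, and a third leaving additional therapies to clinical judgement. The time to resolve this would be short, and the outcomes that section 2.1 names include perinatal death.

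**Working it through.** No stated figure of the protocol bears on this point, so the check is gestation arithmetic followed by a comparison of the sections.

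**Step 1: when randomisation can occur.** From section 6.1, the earliest time is just after (planned gestation minus 7 days) and the latest is (planned gestation minus 1 day).

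| Caesarean planned at | Earliest randomisation | Latest randomisation | Possible before 35+0? |
|---|---|---|---|
| 35+0 | just after 34+0 | 34+6 | yes, the whole window |
| 35+1 | just after 34+1 | 35+0 | yes |
| 35+2 | just after 34+2 | 35+1 | yes |
| 35+3 | just after 34+3 | 35+2 | yes |
| 35+4 | just after 34+4 | 35+3 | yes |
| 35+5 | just after 34+5 | 35+4 | yes |
| 35+6 | just after 34+6 | 35+5 | yes, just under one day |
| 36+0 | just after 35+0 | 35+6 | no |

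Only women planned for 35+0 to 35+6 can be randomised before 35+0. For a caesarean at exactly 35+0 the first dose must also precede 35+0, because section 11.1 wants both doses, 20 to 28 hours apart, given before the caesarean.

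**Step 2: the plan stands.** Sections 2.1 and 4.1 speak of birth, or high risk of birth, before 35+0. A woman with birth planned at 35+0 or later is outside both statements. Section 2.1 also reports that the 2015 Australian and New Zealand guidelines found insufficient evidence for planned caesarean after 34+6. There is no conflict here.

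**Step 3: birth becomes expected before 35+0.** Take a woman given her first dose at 34+2 whose labour starts at 34+4.

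- Sections 2.1 and 4.1: the supported and standard treatment for this birth is a corticosteroid.
- Section 10.3: settles only whether the second blinded dose is given.
- Section 11.1: no further antenatal corticosteroid. The one case it mentions is delay, and it makes no exception for earlier birth.
- Section 12.1.7: additional therapies are at the clinician's discretion, with no reference to section 11.1.
- Section 10.4: emergency unblinding is available, but the protocol does not say that learning the allocation lifts the bar.

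No sentence says which of these prevails.

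**Step 4: size.** The protocol does not give the share of women planned for 35+0 to 35+6, or how many would then deliver before 35+0. As an illustration only:

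- Mothers: 2548 / 1.02 = about 2498.
- Assume 1% to 3% are planned for that week: about 25 to 75 women, half on placebo, so about 12 to 37.
- Assume 5% to 10% of those come to birth before 35+0: 0.05 × 12 = 0.6 to 0.10 × 37 = 3.7, or about 1 to 4 women.

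Both percentages are assumptions without support in the protocol. The calculation also counts every woman planned for that week as randomised before 35+0, which overstates the number.

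**The case against.** The strongest reply is that the boundary is coherent. The title, hypothesis, criteria and strata all define the population by planned caesarean at 35+0 to 39+6, which matches the guideline cut-off quoted in section 2.1. That is correct, and it disposes of three stronger readings.

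- A reader might infer that half the women dosed at 34 weeks get placebo where the protocol itself leaves no equipoise. Sections 2.1 and 4.1 do not say so, because their statements depend on expected birth and not on gestation at the injection.
- A reader might infer that babies born before 35+0 fall outside the trial population and compromise the intention-to-treat analysis. They belong to the population as defined, and so few births could not plausibly move either co-primary result.
- A reader might conclude that 35+0 must be imposed at randomisation. That would make women planned for exactly 35+0 ineligible, although the trial expressly includes them, and it is a clinical choice that this review does not make.

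It can also be said that the protocol already has safeguards: clinician discretion (12.1.7), emergency unblinding (10.4), and the assurance of continuing care according to need (6.3). The bar in section 11.1 also sits under treatment duration and has delay in mind. So the text does not establish that treatment would in fact be withheld. But the discretion clause is general and the bar is specific and unqualified, unblinding does not remove the bar, and the assurance of care stands in the section on withdrawal. These provisions soften the conflict without resolving it.

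**Conclusion.** The point holds in a narrow form. Randomisation and blinded dosing are possible from just after 34+0 for women planned at 35+0 to 35+6. For those whose birth then becomes expected before 35+0, sections 2.1 and 4.1 conflict with section 11.1, and section 12.1.7 does not settle it. If section 11.1 is followed as written, a woman on placebo is denied what the protocol calls standard practice.

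The number of such women cannot be computed from the protocol. It is probably very small, since three things must coincide: randomisation before 35+0, allocation to placebo, and birth expected before 35+0 within days. The sample size and both co-primary analyses are unaffected. The case for acting rests on safety and on sites having one clear instruction.

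**What to change.** Reconcile sections 2.1, 4.1, 6.1, 10.3, 10.4, 11.1 and 12.1.7 for a participant whose birth becomes expected before 35+0. The amended text should state:

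- which provision governs in that case, and how emergency unblinding relates to it;
- whether the 35+0 limit is meant to apply at randomisation as well as at the planned caesarean, so that section 6.1 and the eligibility check in the randomisation program reflect a deliberate choice.

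The clinical rule itself is for the sponsor to decide. The cost is a short amendment and a notice to sites. A change to the randomisation program is needed only if the sponsor chooses to apply the limit at randomisation.
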